A participant will be considered for inclusion in the assessment of an efficacy endpoint if the CSD and Cough Severity VAS are completed on at least 4 days during the 7-day period prior to a post-Baseline visit (other ePROs are completed at the clinic visit only). All efficacy analyses will be conducted based on the observed data only. No imputation is planned for the missing diaries or missing questionnaire items. The pattern of missing is assumed to be missing at random (MAR). The missing pattern will be inspected to determine if the MAR assumption is met. Sensitivity analyses will be implemented to explore the impact of departures from the assumption made in missing diaries.

The longitudinal ANCOVA model (aka. LDA method) assumes that data are missing at random. In this study, it is expected that missing at random and missing completely at random (MAR/MCAR) mechanisms will underlie most of the missingness, and the proportion of data missing not at random (MNAR), driven solely by unobserved values of the study endpoints, will be small.

In addition to the analysis approach specified in the above mentioned primary efficacy endpoint analysis section, the following sensitivity analyses will be used to assess the robustness of the primary analysis approach.

Tipping-point Multiple-imputation Analysis

The Variant 3 of the tipping point as described in paper [Ratitch et al. 2013] will be used. In that approach, missing data are first imputed for all visits under the MAR assumption, and then the worsening/shift is applied. This is repeated with increasing the delta-shift (worsening) until the result is no longer statistically significant. Specifically, for a given constant, c , the tipping point analysis is conducted in a fashion similar to that used in standard multiple imputation, whereby m ($=100$) complete datasets are randomly generated using the original observed dataset. These m complete datasets are subsequently analyzed using the primary model, and the results of those analyses are then combined. The construction and analysis of these m ($=100$) datasets requires four primary steps:

- 1) Using a Markov Chain Monte Carlo method, make the observed dataset monotone-missing. This will be accomplished for each treatment group using “proc mi” within SAS 9.3 or higher by utilizing the options “mcmc chain=multiple impute=monotone;”, in conjunction with all of the covariates (excluding treatment)

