included in the primary analysis model. The random seed will be set equal to 72644243. This step will generate m monotone-missing datasets.

- 2) Applying parametric regression to the monotone-missing datasets, impute all the missing values. This will be accomplished for each treatment group using “proc mi” within SAS 9.3 or higher utilizing the option “monotone reg”, in conjunction with all of the covariates (excluding treatment) included in the primary analysis model. The random seed will be set equal to 72644243. This step will generate m complete datasets.
- 3) To implement the tipping-point aspect of the procedure, subtract a constant c from each of the imputed values of the active arms (to the detriment of active).
- 4) Analyze each of the post-imputation complete datasets using the primary model, obtaining point estimates for the mean of interest (e.g. change-from-baseline treatment difference at 12 weeks) and the associated variance.

Using “proc mianalyze” within SAS 9.3 or higher, the $m=100$ means and variances from the m analyses will be combined to obtain the final test statistic and p-value (Rubin, 1987). The final test statistic $\bar{Q} / (T^{-1/2})$ is approximately distributed as t_v , where \bar{Q} is the sample mean of the m treatment difference estimates, $T = \bar{U} + (m+1) (B/m)$, \bar{U} is the sample mean of the m variance estimates, and B is the sample variance of the m treatment difference estimates. The degrees of freedom, v , will be computed as follows [Barnard and Rubin, 1999]: $v = [(v_1)^{-1} + (v_2)^{-1}]^{-1}$, where $v_1 = (m-1) [1 + (\bar{U}/(1+m^{-1}) B)]^2$ and $v_2 = (1-\gamma) v_0 (v_0 + 1) / (v_0 + 3)$, with $\gamma = (1+m^{-1}) B / T$ and where v_0 represents the complete-data degrees of freedom .

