This procedure will be repeated (using the same m imputed datasets) until the smallest c is found such that the significant result turns non-significant (i.e., $p > 0.05$). This tipping point value c provides a measure of robustness of the primary result. A relatively large value of c implies better robustness of the primary analysis against the impact of missing data in the study. It is noted that when $c=0$ the tipping point analysis described above corresponds to an analysis conducted under the assumption that the missing data are MAR. For values of c larger than 0, the tipping point analyses do not assume that the missing values follow a MAR mechanism. In fact, the analysis is based on a special MNAR mechanism in which all missing data across the arms are assumed to have a worse response by a constant amount of c than the values would have had under MAR.

Jump-to-reference (J2R) Multiple-imputation Analysis

J2R imputation falls under the category of pattern mixture models known as reference-based imputation (RBI). The RBI approach uses different imputation models for missing data in different treatment groups. In J2R, missing data in the control group are imputed under the MAR assumption, while missing data in the treatment groups are imputed under a MNAR assumption using the control group profile for time points after withdrawal.

The following steps will be used to implement the J2R multiple-imputation analysis.

- 1) A parameter-estimation model is fitted using PROC MCMC. All the covariates included in the primary analysis will be used for the parameter-estimation model. For the MCMC procedure, an initial random seed=72644243 will be used. N=500 sets of pseudo-independent samples of the model parameters will be drawn from the joint posterior distribution.

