3.9 SAMPLE SIZE AND POWER CALCULATIONS

The sample size calculations are powered to test the primary efficacy endpoint, with the following assumptions based on the results from a phase 2 chronic cough study. In MK-7264 Protocol 012, the change from baseline in LCQ total score at Week 12 was 1.1 and 1.7 for 20 mg and 50 mg compared to placebo. In this study, given the population is targeted for participants with recent onset chronic cough (< 12 months) which is different from participants with chronic cough (\geq 12 months) in Protocol 012, conservative assumptions were used for sample size calculation:

- Treatment difference in change from baseline in LCQ total score at Week 12 is 1.1 point
- Common SD of change from baseline in LCQ total score is 3.5

Based on the assumptions above, a total of 414 participants (207 participants per intervention group) will provide at least 80% power. The calculation is based on an overall one-sided $\alpha=0.025$ significance level, adjusted for one IA for efficacy ($\alpha=0.001$), and one final efficacy analysis ($\alpha=0.024$). A dropout rate of 15% at Week 12 is accounted for the sample size calculation to ensure 352 evaluable participants complete the Week 12 evaluation.

With assumptions on the AE rates in the placebo group based on the Protocol 012 results, the minimum detectable AE rate differences are 8.4%, 9.0%, and 7.7% in overall taste-related AEs, oral paresthesia AEs, and oral hypoesthesia AEs, respectively.

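### The tipping-point analysis shifts only the gefapixant arm in step 3 but is then described as shifting missing data in all arms, so the reported c is not uniquely defined

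*Combined protocol and SAP*

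**What the plan says.** sSAP section 3.6.1 names two sensitivity analyses for the primary endpoint: a tipping-point multiple imputation and a jump-to-reference multiple imputation. The tipping-point text has four relevant parts.

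- **Summary of the method.** It says that "missing data are first imputed for all visits under the MAR assumption, and then the worsening/shift is applied". No arm is named.
- **Algorithm.** Constructing and analysing the "datasets requires four primary steps". Step 3 is to "subtract a constant c from each of the imputed values of the active arms (to the detriment of active". Placebo imputations are left as they were under MAR.
- **Reported result.** The procedure is repeated until the smallest c giving p > 0.05 is found. The text adds that "A relatively large value of c implies better robustness of the primary analysis".
- **Description of the assumption.** For c above zero, the mechanism is said to be one in which "all missing data across the arms are assumed to have a worse response by a constant amount of c".

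There is a single constant c throughout. No separate placebo shift and no grid are defined in section 3.6.1.

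**The concern.** The closing description is untrue of step 3. Under step 3 the missing placebo values are not worsened at all. The trial has one active and one control arm, so the natural reading of the closing sentence includes placebo.

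The two rules test different departures from MAR. Shifting gefapixant alone asks how much worse its dropouts would have to be than MAR predicts before the result is lost. Shifting both arms by the same c asks about a common worsening. That moves the treatment difference only through any imbalance in missingness between arms. With similar missingness, the estimate hardly moves and significance is lost mainly because the standard error grows. This has some value, but it says little about poor outcomes specific to gefapixant dropouts.

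Two programmers could therefore obtain different values of c from the same data. Alternatively, a value from step 3 could be reported with the wrong assumption attached. The sentence equating a large c with robustness suits step 3. Applied to the equal shift, it could overstate what has been shown.

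**Working it through.** **Inputs.** From sSAP section 3.9: "Treatment difference in change from baseline in LCQ total score at Week 12 is 1.1 point"; common SD 3.5; 207 per arm; and "A dropout rate of 15% at Week 12 is accounted for the sample size calculation". From section 3.6.1: stop at two-sided p > 0.05 (z = 1.960). From section 3.4.3: the LCQ total runs from 3 to 21, a span of 18 points. The plan gives no missingness by arm, so every split below is an assumption, as is an observed difference equal to the planning value.

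**Plan's own figures.** 414 × 0.85 = 351.9, agreeing with 352 evaluable. With 176 per arm, difference 1.1, SD 3.5 and one-sided alpha 0.024, power is 83.4%, consistent with the stated minimum of 80%. The plan states no value of c.

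**Formulas.** Let a and p be the missing proportions on gefapixant and placebo.

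- Difference, active-only shift: 1.1 − a·c
- Difference, same shift in both arms: 1.1 − (a − p)·c
- Variance: 3.5²/[207(1 − a)] + 3.5²/[207(1 − p)], plus a(1 − a)c²/207 for a shifted gefapixant arm and p(1 − p)c²/207 for a shifted placebo arm

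This is a large-sample approximation that ignores baseline and Week 6 information.

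**Worked case, 15% missing in each arm.** At c = 0 the variance is 2 × 12.25/(207 × 0.85) = 0.1392, so SE = 0.373 and z = 1.1/0.373 = 2.95.

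- Active only, c = 2.4: difference 1.1 − 0.15 × 2.4 = 0.74; SE 0.378; z = 1.96. The result tips.
- Both arms, c = 11.95: difference still 1.10; SE 0.561; z = 1.96. The result tips only through the SE, at a shift of about two thirds of the LCQ span (11.95/18 = 0.66).

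**Other splits.**

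| Missing, gefapixant / placebo | Tipping c, active only | Tipping c, both arms | Ratio | At c = 3, active only | At c = 3, both arms |
|---|---|---|---|---|---|
| 15% / 15% | 2.4 | 11.9 | 5.0 | 0.65, p = 0.088 | 1.10, p = 0.005 |
| 18% / 12% | 2.0 | 4.9 | 2.5 | 0.56, p = 0.14 | 0.92, p = 0.018 |
| 20% / 10% | 1.8 | 3.3 | 1.9 | 0.50, p = 0.19 | 0.80, p = 0.039 |
| 25% / 5% | 1.4 | 1.8 | 1.2 | 0.35, p = 0.37 | 0.50, p = 0.20 |

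At c = 3 the conclusion reverses in the first three rows and not in the fourth.

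**Sensitivity at 15% / 15%** (active only vs both arms). Observed difference 0.9: 1.1 vs 7.6; 1.4: 4.3 vs 17.4. SD 3.0: 3.0 vs 13.1; SD 3.7: 2.1 vs 11.4. If placebo lost more participants, the equal shift would raise the estimated difference. At 13% / 17% it tips only at 34.5, beyond the LCQ span, against 2.8 for active only. Nothing in the documents points to that split.

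**Check by simulation.** Regression imputation within arm, m = 100, Rubin's rules with the sSAP's degrees of freedom, 40 replicates per setting, Week 6 to Week 12 correlation of 0 and 0.6. Median tipping c, active only vs both arms: 15% / 15%, 2.4–2.5 vs 11.9–12.1; 20% / 10%, 1.8–2.0 vs 3.4–3.6; 25% / 5%, 1.5–1.6 vs 1.8–1.9. These agree with the closed form.

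**The case against.** The best reply is that the algorithm itself is clear. Step 3 names the arm, the operation and the direction, and the stopping rule repeats that procedure. The disputed sentence is later commentary and gives no programming instruction. The section also uses plurals loosely for the single gefapixant arm, so the sentence may simply have been meant for the active arm. That stands as far as it goes: step 3 governs, its reading of a large c is sound, and if loose wording is the explanation, correcting one sentence is enough. It does not make the sentence correct, and the sentence is where a reader learns what departure from MAR was assumed.

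The size of the conflict also rests on assumed missingness. Taste-related events are the most frequent adverse events (protocol section 2.3), and dysgeusia is dose-related (protocol section 4.3). Losses may therefore be heavier on gefapixant, which is where the two rules converge. No rates by arm are given, so this shows direction only. It is a reason to read the five-fold ratio as the equal-missingness case and not as a forecast.

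Finally, jump-to-reference covers poor outcomes in gefapixant dropouts separately: "missing data in the treatment groups are imputed under a MNAR assumption using the control group profile". That is so, but it does not make the reported c unambiguous. A two-parameter grid goes beyond what reconciling the text strictly requires.

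**Conclusion.** The concern holds. The current sSAP gives two incompatible descriptions of one sensitivity analysis with one constant c. Under the planning difference and SD, the tipping values differ by a factor of 5.0 at equal missingness, falling to 1.2 at 25% / 5%. The mismatch in the text is certain. Its practical size depends on arm-specific missingness, which the plan does not give, and on the observed difference. It also requires the closing sentence to be programmed, or used to describe a step 3 result. The consequence is confined to the tipping-point analysis and its interpretation. It should be corrected, but it does not threaten the trial's main conclusion.

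**What to change.** **Minimum.** Rewrite the closing sentence so that it says what step 3 does: missing gefapixant values are worse than MAR predicts by c, and missing placebo values stay at MAR. This is a wording change only.

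**Preferred.** Define two shifts, c_gefapixant and c_placebo, over a stated grid that includes c_placebo = 0, which is the present step 3. Describe the assumption in those terms, limit the statement that a large c means robustness to the c_placebo = 0 line, and report the grid with observed missingness by arm. The sSAP's summary of changes mentions a two-dimensional version; it is cited here only because the grid fits that recorded intent. The cost is a second loop in the existing program, with no change to data collection or the primary model.

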3.6.2 Statistical Methods for Safety Analyses

Safety and tolerability will be assessed by clinical review of all relevant parameters including AEs, laboratory tests, and vital signs.

The analysis of safety results will follow a tiered approach (Table 2). The tiers differ with respect to the analyses that will be performed. Adverse events (specific terms as well as system organ class terms) and events that meet predefined limits of change in laboratory and vital signs are either prespecified as “Tier 1” endpoints, or will be classified as belonging to “Tier 2” or “Tier 3” based on the observed proportions of participants with an event.

Tier 1 Events

Safety parameters or adverse events of interest that are identified a priori constitute “Tier 1” safety endpoints that will be subject to inferential testing for statistical significance with p-values and 95% CIs to be provided for between-treatment differences in the proportion of participants with events; these analyses will be performed using the Miettinen and Nurminen (M&N) method (1985) [Miettinen, O. and Nurminen, M. 1985], an unconditional, asymptotic method. For this protocol, taste-related AEs (including dysgeusia, ageusia, hypogeusia, hypergeusia, and taste disorder) are considered Tier 1 events.

Tier 2 Events

Tier 2 parameters will be assessed via point estimates and 95% CIs provided for differences in the proportion of participants with events.

Membership in Tier 2 requires that at least 4 participants in any treatment group exhibit the event. The threshold of at least 4 events was chosen because the 95% confidence interval for the between-group difference in percent incidence will always include zero when treatment groups of equal size each have less than 4 events and, thus, would add little to the interpretation of potentially meaningful differences. Because many 95% confidence intervals for Tier 2 events may be provided without adjustment for multiplicity, the confidence intervals should be regarded as a helpful descriptive measure to be used in review, not a formal method for assessing the statistical significance of the between-group differences in adverse events and safety parameters that meet predefined limits of change.

In addition to individual events that occur in 4 or more participants in any treatment group, any oral paresthesia AE, any oral hypoesthesia AE, and the broad AE categories consisting of the proportion of participants with any AE, a drug-related AE, a serious AE, an AE which is both drug-related and serious, and discontinuation due to an AE will be considered Tier 2 events.

Tier 3 Events

Safety endpoints that are not Tier 1 or 2 events are considered Tier 3 events. Only point estimates by treatment group are provided for Tier 3 safety parameters.

Continuous Safety Measures

For continuous measures such as changes from baseline in laboratory and vital signs, summary statistics for baseline, on-treatment, and change from baseline values will be provided by intervention group in table format.

The frequency of taste-related AEs across pre-defined time intervals will be provided, where the time intervals will be defined as: >0 to ≤1 week, >1 to ≤4 weeks, >4 to ≤8 weeks, and >8 to ≤12 weeks. In each time interval, the denominator for calculation of percentage will be the number of participants treated during the time interval and the numerator will be the number of participants with at least one taste-related AE occurring in this time interval.

Table 2 Analysis Strategy for Safety Parameters

Safety Tier	Safety Endpoint ^a	p-Value	95% CI for Treatment Comparison	Descriptive Statistics
Tier 1	Any taste-related AE (including dysgeusia, ageusia, hypogeusia, hypergeusia, and taste disorder)	X	X	X
Tier 2	Any oral paresthesia AE		X	X
	Any oral hypoesthesia AE		X	X
	Any AE		X	X
	Any Serious AE		X	X
	Any Drug-related AE		X	X
	Any Serious and Drug-related AE		X	X
	Discontinuation due to AE		X	X
	Specific AEs, SOCs, or PDLCs ^b (incidence ≥4 participants in one of the treatment groups)		X X	X X
Tier 3	Time to Onset from the First Dosing Date and Duration of Event for Taste-Related AEs			X
	Frequency of Taste-Related AEs for Time Intervals: >0 to ≤1 Week, >1 to ≤4 Weeks, >4 to ≤8 Weeks, and >8 to ≤12 Weeks			X
	Specific AEs, SOCs or PDLCs ^b (incidence <4 participants in all of the treatment groups)			X
	Change from Baseline Results (Labs, Vital Signs)			X

AE = adverse event; CI = confidence interval; PDLC = predefined limit of change; SOC = system organ class; X = results will be provided.

^a Adverse experience references refer to both clinical and laboratory AEs.

^b Includes only those endpoints not prespecified as Tier 1 or not already prespecified as Tier 2 endpoints.

Table 3 Predefined Limit of Change from Baseline

Laboratory Test	Criteria
hematocrit	↓ ≥20% and <LLN ↑ ≥20% and >ULN
WBC	↓ ≥20% and <LLN ↑ ≥20% and >ULN
Platelet	↓ ≥25% and <LLN ↑ ≥50% and >ULN
Bilirubin	↑ ≥100% and >ULN ↑ ≥50% and >1.5x ULN ↑ ≥50% and >2x ULN >3x ULN >5x ULN
AST	↑ ≥100% and >ULN ↑ ≥50% and >1.5x ULN ↑ ≥50% and >2x ULN >3x ULN >5x ULN
ALT	↑ ≥100% and >ULN ↑ ≥50% and >1.5x ULN ↑ ≥50% and >2x ULN >3x ULN >5x ULN
Neutrophil	↓ ≥20% and <LLN ↑ ≥20% and >ULN
BUN	↑ ≥50% ↑ ≥20% and BLN >ULN
Serum creatinine	↑ ≥50% ↑ ≥20% and BLN >ULN
ALT = alanine aminotransferase; AST = aspartate aminotransferase; BLN = baseline; BUN = blood urea nitrogen; LLN = Lower limit of normal range; ULN = Upper limit of normal range; WBC = white blood cell.	

3.6.3 Summaries of Baseline Characteristics, Demographics, and Other Analyses

3.6.3.1 Demographic and Baseline Characteristics

The comparability of the treatment groups for each relevant demographic and baseline characteristic will be assessed by the use of tables and/or graphs. No statistical hypothesis tests will be performed on these characteristics. The number and percentage of participants screened and randomized and the primary reasons for screening failure and discontinuation will be displayed. Demographic variables (eg, age, gender, race, weight, and height), baseline characteristics, primary and secondary diagnoses, and prior and concomitant therapies will be summarized by treatment either by descriptive statistics or categorical tables.

3.7 INTERIM ANALYSES

[figure not shown]
Results of all interim analyses will be reviewed by an external DMC, which will make recommendations to the EOC of the Sponsor to continue, modify or stop the study.

3.7.1 Interim Efficacy Analysis

One planned efficacy IA will be conducted when approximately 40% of target participants (approximately the first 166 enrolled participants) have either completed the study

(approximately 141 enrolled participants) or discontinued study intervention early. All available data will be included in the analysis, including follow-up data and partial data from participants enrolled after the participants triggering the IA.

The purpose of the IA is to allow early stop for strong benefit (efficacy) or for futility. The efficacy IA will be based on the primary endpoint of the LCQ change from baseline in total score at Week 12.

3.7.2 Interim Safety Analyses

Interim safety will also be assessed at the time of prespecified IA for futility, ie, when approximately 40% of target participants (approximately the first 166 enrolled participants) have either completed the study or discontinued the study intervention early. A general review of safety results will be performed based on review of AEs, laboratory safety parameters, and other safety endpoints.

3.8 MULTIPLICITY

Other than an adjustment to the alpha level for the IA for efficacy, no multiplicity adjustment is planned.

3.9 SAMPLE SIZE AND POWER CALCULATIONS

The sample size calculations are powered to test the primary efficacy endpoint, with the following assumptions based on the results from a phase 2 chronic cough study. In MK-7264 Protocol 012, the change from baseline in LCQ total score at Week 12 was 1.1 and 1.7 for 20 mg and 50 mg compared to placebo. In this study, given the population is targeted for participants with recent onset chronic cough (< 12 months) which is different from participants with chronic cough (\geq 12 months) in Protocol 012, conservative assumptions were used for sample size calculation:

- Treatment difference in change from baseline in LCQ total score at Week 12 is 1.1 point
- Common SD of change from baseline in LCQ total score is 3.5

Based on the assumptions above, a total of 414 participants (207 participants per intervention group) will provide at least 80% power. The calculation is based on an overall one-sided $\alpha=0.025$ significance level, adjusted for one IA for efficacy ($\alpha=0.001$), and one final efficacy analysis ($\alpha=0.024$). A dropout rate of 15% at Week 12 is accounted for the sample size calculation to ensure 352 evaluable participants complete the Week 12 evaluation.

With assumptions on the AE rates in the placebo group based on the Protocol 012 results, the minimum detectable AE rate differences are 8.4%, 9.0%, and 7.7% in overall taste-related AEs, oral paresthesia AEs, and oral hypoesthesia AEs, respectively.

